### Management of Pneumonitis

- For Grade 2 events, treat with systemic corticosteroids. When symptoms improve to Grade 1 or less, steroid taper should be started and continued over no less than 4 weeks.
- For Grade 3-4 events, immediately treat with intravenous steroids. Administer additional anti- inflammatory measures, as needed.
- Add prophylactic antibiotics for opportunistic infections in the case of prolonged steroid administration.

### Management of Diarrhea/Colitis

Subjects should be carefully monitored for signs and symptoms of enterocolitis (such as diarrhea, abdominal pain, blood or mucus in stool, with or without fever) and of bowel perforation (such as peritoneal signs and ileus).

- All subjects who experience diarrhea/colitis should be advised to drink liberal quantities of clear fluids. If sufficient oral fluid intake is not feasible, fluid and electrolytes should be substituted via IV infusion. For Grade 2 or higher diarrhea, consider GI consultation and endoscopy to confirm or rule out colitis.
- For Grade 2 diarrhea/colitis that persists greater than 3 days, administer oral corticosteroids.
- For Grade 3 or 4 diarrhea/colitis that persists > 1 week, treat with intravenous steroids followed by high dose oral steroids.
- When symptoms improve to Grade 1 or less, steroid taper should be started and continued over no less than 4 weeks.

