**Table 2: Dose Modification and Toxicity Management Guidelines for Immune-related AEs Associated with Pembrolizumab**  
**General instructions:**

1. Corticosteroid taper should be initiated upon AE improving to Grade 1 or less and continue to taper over at least 4 weeks.
2. For situations where pembrolizumab has been withheld, pembrolizumab can be resumed after AE has been reduced to Grade 1 or 0 and corticosteroid has been tapered. Pembrolizumab should be permanently discontinued if AE does not resolve within 12 weeks of last dose or corticosteroids cannot be reduced to  $\leq 10$  mg prednisone or equivalent per day within 12 weeks.
3. For severe and life-threatening irAEs, IV corticosteroid should be initiated first followed by oral steroid. Other immunosuppressive treatment should be initiated if irAEs cannot be controlled by corticosteroids.

Immune-related AEs	Toxicity grade or conditions (CTCAEv4.0)	Action taken to pembrolizumab	irAE management with corticosteroid and/or other therapies	Monitor and follow-up
Pneumonitis	Grade 2	Withhold	
 
Administer corticosteroids (initial dose of 1-2 mg/kg prednisone or equivalent) followed by taper
 
	
 
Monitor participants for signs and symptoms of pneumonitis
 
Evaluate participants with suspected pneumonitis with radiographic imaging and initiate corticosteroid treatment
 
Add prophylactic antibiotics for opportunistic infections
 

	Grade 3 or 4, or recurrent Grade 2	Permanently discontinue		
Diarrhea / Colitis	Grade 2 or 3	Withhold	
 
Administer corticosteroids (initial dose of 1-2 mg/kg prednisone or equivalent) followed by taper
 
	
 
Monitor participants for signs and symptoms of enterocolitis (ie, diarrhea, abdominal pain, blood or mucus in stool with or without fever) and of bowel perforation (ie, peritoneal signs and ileus).
 
Participants with <math>\geq</math> Grade 2 diarrhea suspecting colitis should consider GI consultation and performing endoscopy to rule out colitis.
 
Participants with diarrhea/colitis should be advised to drink liberal quantities of clear fluids. If sufficient oral fluid intake is not feasible, fluid and electrolytes should be substituted via IV infusion.
 

	Grade 4	Permanently discontinue		

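### Section 7.5 and Table 2 conflict on when steroids start for pembrolizumab-related diarrhea/colitis, and nothing says which governs

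*Combined protocol and SAP*

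**What the plan says.** Section 7.5, Management of Diarrhea/Colitis, makes steroids depend on how long the event has lasted. For the milder grade: "For Grade 2 diarrhea/colitis that persists greater than 3 days, administer oral corticosteroids". For the severe grades: "For Grade 3 or 4 diarrhea/colitis that persists > 1 week, treat with intravenous steroids followed by high dose oral steroids". It then sets the taper: "When symptoms improve to Grade 1 or less, steroid taper should be started and continued over no less than 4 weeks". The same subsection advises fluids, suggests GI consultation and endoscopy from Grade 2, and asks for monitoring for bowel perforation.

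Section 5.4, Table 2, Diarrhea / Colitis row, has no duration condition: "Administer corticosteroids (initial dose of 1-2 mg/kg prednisone or equivalent) followed by taper". Its general instruction 3 adds: "For severe and life-threatening irAEs, IV corticosteroid should be initiated first followed by oral steroid". General instruction 1 on the taper agrees with Section 7.5: "Corticosteroid taper should be initiated upon AE improving to Grade 1 or less and continue to taper over at least 4 weeks". General instruction 2 says that after a hold "pembrolizumab can be resumed after AE has been reduced to Grade 1 or 0 and corticosteroid has been tapered".

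On the standing of the two sections, Section 5.4 names Tables 2 and 3 as the source for managing immune-related toxicity and also refers to a separate pembrolizumab guidance document for supportive care, including steroids. Its opening paragraph stresses that prompt treatment limits complications. The introduction to Section 7.5 describes its measures as suggestions and applies them once the investigator has judged the event to be related to pembrolizumab.

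**The concern.** The two sections address the same patient and the same event but give different starting points for steroids. A clinician who opens Table 2 and one who opens Section 7.5 could treat the same Grade 3 event a week apart, each following the protocol. The risk is to the patient: Section 7.5 itself names perforation as a complication to watch for, and the trial population has potentially curable disease.

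Who reads which page also matters. Section 5.4 notes that immune-related events can appear months after the last dose. Section 6.3.2 allows adverse events to be collected by phone while patients receive chemotherapy at their own physician's office. Written guidance therefore has to be unambiguous for staff who do not work with the protocol every day.

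**Working it through.** No sample size, power or error rate is involved. The check is a comparison of the two sections, followed by one piece of calendar arithmetic.

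**Step 1: the instructions side by side**

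| Item | Section 7.5 | Section 5.4, Table 2 |
|---|---|---|
| Grade 2 | Oral steroid after more than 3 days | 1-2 mg/kg prednisone or equivalent, no wait stated |
| Grade 3 | IV then high-dose oral after more than 7 days | 1-2 mg/kg, no wait stated; IV first if severe |
| Grade 4 | As Grade 3 | IV first if life-threatening, no wait stated |
| Taper | At least 4 weeks | At least 4 weeks |
| Pembrolizumab | Not addressed | Withhold for Grade 2-3; stop permanently for Grade 4 |

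In the extracted Table 2 the steroid cell sits on the Grade 2-3 line and the Grade 4 cell is blank, probably because the cell was merged. General instruction 3 covers Grade 4 in any case.

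**Step 2: is there a rule of precedence?** None was found. Section 5.4 points to its tables and to an outside document. Section 7.5 calls itself suggested. Neither statement says which steroid trigger applies when the two differ.

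**Step 3: does the wait fit the rest of Section 7.5?** The section directs steroids for six organ toxicities: pneumonitis, diarrhea/colitis, hypophysitis, hyperthyroidism, hepatic toxicity and renal failure/nephritis. Only diarrhea/colitis, 1 of 6, makes them conditional on persistence. Grade 3-4 pneumonitis is to be treated at once. Within the diarrhea/colitis bullets the order is also inverted: the more severe grades have the longer wait (more than 7 days against more than 3).

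**Step 4: what does following Table 2 do to dose 2?** The inputs are a 21-day cycle with a window of 3 days either side for C2D1 (Study Schema) and a taper of at least 4 weeks (Table 2, general instruction 1).

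- Latest dose 2 = 21 + 3 = 24 days after C1D1.
- Shortest taper = 4 x 7 = 28 days.
- Shortfall = 28 - 24 = 4 days, even if the taper began on C1D1 itself.

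If the word tapered in general instruction 2 means that the taper is complete, any cycle-1 event treated with steroids rules out dose 2. Section 5.4 then ends study treatment, and the Study Schema ties the RT boost to dose 2, so the boost goes too.

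The two sections therefore differ on dose 2 only for a cycle-1 Grade 2-3 event that resolves before the Section 7.5 threshold and in time for dose 2. Table 2 would have started steroids and Section 7.5 would not. For longer events both sections require the same minimum taper. Grade 4 stops pembrolizumab either way.

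**The case against.** The strongest reply is that Section 7.5 is advisory. It leaves supportive care to the treating investigator's judgment, calls its measures suggestions and does not prohibit earlier steroids. A reader might infer that it requires a week without steroids; the text does not say that. Nor does Table 2 say that steroids start at once; it is silent on timing. These points stand, and they limit the finding to a conflict in stated triggers. They do not remove it, because Section 7.5 offers no other steroid trigger for diarrhea/colitis.

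A second reply is that the wait allows for diagnosis. Section 7.5 asks that infection and other causes be excluded and suggests endoscopy to settle whether colitis is present. For Grade 2 this is plausible. As an explanation of the Grade 3-4 wait it is weak, because the section applies its guidelines only after the event has been attributed to pembrolizumab.

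A third reply is that the outside guidance document may settle the matter. It was not available for this review. The documents show a mismatch; they do not show that Table 2 is right for Grade 2. That is a clinical choice for the sponsor, and it is why the Grade 2 edit should wait for the check.

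A reader might also infer a fixed day of onset after which dose 2 is no longer at issue. The documents support no such cut-off: an event that starts late in cycle 1 but resolves quickly can still be over by day 24.

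**Conclusion.** The conflict is real and sits in two current sections. For Grade 3-4 events the stated wait is more than 7 days against none; for Grade 2 it is more than 3 days against none. This is a patient-safety inconsistency that should be corrected at the next amendment.

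The conclusion rests on reading the Section 7.5 bullets as the section's only steroid triggers for diarrhea/colitis, which is what they are as written. The dose-2 consequence rests further on reading tapered as taper completed.

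A reader might go on to infer harm to an expected number of patients, or an effect on the feasibility endpoint or the TIL analysis. The documents give no rate for such events, so no patient count is claimed, and no statistical figure changes.

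**What to change.** **Grade 3-4.** In Section 7.5, Management of Diarrhea/Colitis, delete the one-week persistence condition, so that IV steroids start once the event is judged immune-related.

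**Grade 2.** Align the bullet itself with Table 2, so that a clinician reading it no longer sees a contradictory wait. Any precedence wording should be limited to this toxicity, for example: *For diarrhea/colitis, Table 2 governs when corticosteroids are started.* The sponsor should first check this edit against the guidance document cited in Section 5.4.

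**What to avoid.** Do not add a sentence giving Table 2 precedence over all of Section 7.5. For Grade 3-4 hyperthyroidism, Section 7.5 directs IV then oral steroid, whereas Table 2 lists only beta-blockers or thionamides. A general rule would displace that steroid instruction without anyone having decided to do so.

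**Cost.** One deleted phrase and one aligned bullet at the next amendment, with no new procedures, data fields or patients. The consequence to accept is that a short-lived cycle-1 Grade 2-3 event treated under Table 2 forfeits dose 2 and the RT boost. Table 2 and the discontinuation rule in Section 5.4 already imply this, but the sponsor should adopt it knowingly, above all for Grade 2.

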### Management of Type 1 diabetes mellitus (if new onset, including diabetic ketoacidosis [DKA]) or $\geq$ Grade 3 Hyperglycemia, if associated with ketosis (ketonuria) or metabolic

### **acidosis (DKA)**

- For T1DM or Grade 3-4 Hyperglycemia
- Insulin replacement therapy is recommended for Type I diabetes mellitus and for Grade 3-4 hyperglycemia associated with metabolic acidosis or ketonuria.
- Evaluate patients with serum glucose and a metabolic panel, urine ketones, glycosylated hemoglobin, and C-peptide.

### **Management of Hypophysitis**

- For Grade 2 events, treat with corticosteroids. When symptoms improve to Grade 1 or less, steroid taper should be started and continued over no less than 4 weeks. Replacement of appropriate hormones may be required as the steroid dose is tapered.
- For Grade 3-4 events, treat with an initial dose of IV corticosteroids followed by oral corticosteroids. When symptoms improve to Grade 1 or less, steroid taper should be started and continued over no less than 4 weeks. Replacement of appropriate hormones may be required as the steroid dose is tapered.

### **Management of Hyperthyroidism or Hypothyroidism**

Thyroid disorders can occur at any time during treatment. Monitor patients for changes in thyroid function (at the start of treatment, periodically during treatment, and as indicated based on clinical evaluation) and for clinical signs and symptoms of thyroid disorders.

- Grade 2 hyperthyroidism events (and Grade 3-4 hypothyroidism):
  - In hyperthyroidism, non-selective beta-blockers (e.g. propranolol) are suggested as initial therapy.
  - In hypothyroidism, thyroid hormone replacement therapy, with levothyroxine or liothyronine, is indicated per standard of care.
- Grade 3-4 hyperthyroidism. Treat with an initial dose of IV corticosteroid followed by oral corticosteroids. When symptoms improve to Grade 1 or less, steroid taper should be started and continued over no less than 4 weeks. Replacement of appropriate hormones may be required as the steroid dose is tapered.

### **Management of Hepatic toxicities**

- For Grade 2 events, monitor liver function tests more frequently until returned to baseline values (consider weekly).
  - Treat with IV or oral corticosteroids
- For Grade 3-4 events, treat with intravenous corticosteroids for 24 to 48 hours.
- When symptoms improve to Grade 1 or less, a steroid taper should be started and continued over no less than 4 weeks.

### **Management of Renal Failure or Nephritis**

- For Grade 2 events, treat with corticosteroids.
- For Grade 3-4 events, treat with systemic corticosteroids.
- When symptoms improve to Grade 1 or less, steroid taper should be started and continued over no less than 4 weeks.

### **Management of Infusion Reactions**

Signs and symptoms usually develop during or shortly after drug infusion and generally resolve completely within 24 hours of completion of infusion.

Table 5 shows treatment guidelines for subjects who experience an infusion reaction associated with administration of pembrolizumab.

### **Table 5: Pembrolizumab Infusion Reaction Treatment Guidelines**

NCI CTCAE Grade	Treatment	Premedication at subsequent dosing
Grade 1  Mild reaction; infusion interruption not indicated; intervention not indicated	Increase monitoring of vital signs as medically indicated until the subject is deemed medically stable in the opinion of the investigator.	None
Grade 2  Requires infusion interruption but responds promptly to symptomatic treatment (e.g., antihistamines, NSAIDS, narcotics, IV fluids); prophylactic medications indicated for < =24 hrs.	
Stop Infusion and monitor symptoms.
 
Additional appropriate medical therapy may include but is not limited to:
 
IV fluids Antihistamines NSAIDS Acetaminophen Narcotics
 
Increase monitoring of vital signs as medically indicated until the subject is deemed medically stable in the opinion of the investigator.
 
If symptoms resolve within one hour of stopping drug infusion, the infusion may be restarted at 50% of the original infusion rate (e.g., from 100 mL/hr to 50 mL/hr). Otherwise dosing will be held until symptoms resolve and the subject should be premedicated for the next scheduled dose.
 
Subjects who develop Grade 2 toxicity despite adequate premedication should be permanently discontinued from further trial treatment administration.
	
Subject may be premedicated 1.5h (<math>\pm</math> 30 minutes) prior to infusion of pembrolizumab (MK- 3475) with:
 
Diphenhydramine 50 mg po (or equivalent dose of antihistamine).
 
Acetaminophen 500-1000 mg po (or equivalent dose of antipyretic).

Grades 3 or 4  Grade 3: Prolonged (i.e., not rapidly responsive to symptomatic	
Stop Infusion.
 
Additional appropriate medical therapy may
	No subsequent dosing


medication and/or brief interruption of infusion); recurrence of symptoms following initial improvement; hospitalization indicated for other clinical sequelae (e.g., renal impairment, pulmonary infiltrates)
 
Grade 4: Life-threatening; pressor or ventilatory support indicated
	
include but is not limited to:
 
IV fluids Antihistamines NSAIDS Acetaminophen Narcotics Oxygen Pressors Corticosteroids Epinephrine
 
Increase monitoring of vital signs as medically indicated until the subject is deemed medically stable in the opinion of the investigator.
 
Hospitalization may be indicated. Subject is permanently discontinued from further trial treatment administration.
	

Appropriate resuscitation equipment should be available in the room and a physician readily available during the period of drug administration.
		

## 7.6 Reporting Requirements for Adverse Events

### 7.6.1 Steps to Determine If an Adverse Event Requires Expedited Reporting

Step 1: Identify the type of adverse event using the NCI Common Terminology Criteria for Adverse Events (CTCAE VERSION 4.0).

Step 2: Grade the adverse event using the NCI CTCAE VERSION 4.0

Step 3: Determine whether the adverse event is related to the protocol therapy

**Attribution categories are as follows:**

- Definite – The AE is *clearly related* to the study treatment.
- Probable – The AE is *likely related* to the study treatment.
- Possible – The AE *may be related* to the study treatment.
- Unlikely – The AE is doubtfully related to the study treatment.
- Unrelated – The AE is *clearly NOT related* to the study treatment.

Note: This includes all events that occur within 90 days of the last dose of protocol treatment (pembrolizumab and RT). Any event that occurs more than 90 days after the last dose of treatment (pembrolizumab and/or RT) and is attributed (possibly, probably, or definitely) to the agent(s) must also be reported accordingly.

Step 4: Determine the prior experience of the adverse event.

Expected events are those that have been previously identified as resulting from administration of the agent. An adverse event is considered unexpected, for expedited reporting purposes only, when either the type of event or the severity of the event is not listed in:

- the current known adverse events listed in the Agent Information Section of this protocol;
- the drug package insert;
- the current Investigator's Brochure

#### **7.6.2 Expedited Reporting**

**7.6.2.1** The Principal Investigator must be notified by study staff or co-investigators within 24 hours of learning of any serious adverse events, regardless of attribution, occurring during the study or within 30 days of the last administration of the study drug.

Phone Number for Expedited Reporting:

[name], PhD  
[contact]

Alternate Phone Number for Expedited Reporting:

[name]  
[contact]

Serious Adverse Event deemed to be related to the protocol and on-study deaths, including death of a research subject unless the death is expected (e.g. due to disease progression) to be reported to the DSMC within 24 hours for medical monitor ad hoc review between meetings to determine if immediate action is required. Reports may be emailed to the DSMC Admin at [[contact]](mailto:[contact]).

#### **7.6.2.2 Reporting to the Institutional Review Board (IRB)**

The IRB must be notified within 10 business days of "any unanticipated problems involving risk to subjects or others."

1. Any serious event (injuries, side effects, deaths or other problems), which in the opinion of the Principal Investigator was unanticipated, involved risk to subjects or others, and was possibly related to the research procedures.
2. Any serious accidental or unintentional change to the IRB-approved protocol that alters the level of risk.
3. Any deviation from the protocol taken without prior IRB review to eliminate apparent immediate hazard to a research subject.
4. Any new information (e.g., publication, safety monitoring report, updated sponsor safety report), interim result or other finding that indicates an unexpected change to the risk/benefit ratio for the research.
5. Any breach in confidentiality that may involve risk to the subject or others.
6. Any complaint of a subject that indicates an unanticipated risk or that cannot be resolved by the Principal Investigator.

#### **7.6.3 Routine Reporting**

All other adverse events- such as those that are expected, or are unlikely or definitely not related to the study participation are to be reported annually as part of regular continuing reviews or data submissions.

#### **7.6.4 Reporting to the Food and Drug Administration**

The investigator or his designee must submit SAEs on FDA Form 3500A (MedWatch) according to the following reporting criteria:

- Reporting any unexpected fatal or life-threatening suspected adverse reactions no later than 7 calendar days after initial receipt of the information
- Reporting any (1) serious, unexpected suspected adverse reactions (SUSAR), (2) findings from other clinical, animal, or in-vitro studies that suggest significant human risk, and (3) a clinically important increase in the rate of a serious suspected adverse reaction no later than 15 calendar days after determining that the information qualifies for reporting

### **7.7 Reporting to US Army Medical Research and Material Command Office (USAMRMC) of Research Protections (ORP) Human Research Protection Office (HRPO)**

The protocol will not be initiated until written notification of approval of the research project is issued by the USAMRMC ORP HRPO.

(1) Substantive modifications to the research protocol and any modifications that could potentially increase risk to subjects must be submitted to the HRPO for approval prior to implementation. The USAMRMC ORP HRPO defines a substantive modification as a change in Principal Investigator, change or addition of an institution, elimination or alteration of the consent process, change to the study population that has regulatory implications (e.g. adding children, adding active duty population, etc), significant change in study design (i.e. would prompt additional scientific review) or a change that could potentially increase risks to subjects.

(2) Any changes of the IRB used to review and approve the research will be promptly reported to the USAMRMC ORP HRPO.

(3) All unanticipated problems involving risk to subjects or others must be promptly reported:

by [contact]),  
by email ([contact]), or  
by [contact]) to the HRPO.

A complete written report will follow the initial notification. In addition to the methods above, the complete report can be sent to the US Army Medical Research and Materiel Command,

ATTN: MCMR-RP,  
[name],  
[name].

(4) Suspensions, clinical holds (voluntary or involuntary), or terminations of this research by the Institutional Review Board (IRB), the institution, the Sponsor, or regulatory agencies will be promptly reported to the USAMRMC ORP HRPO.

(5) A copy of the continuing review approval notification by the IRB of Record must be submitted to the HRPO as soon as possible after receipt. For greater than minimal risk research, a copy of the continuing review report approved by the IRB must also be provided. Please note that the HRPO also conducts random audits at the time of continuing review. Additional information and documentation may be requested at that time.

(6) The final study report, including any acknowledgement documentation and supporting documents, must be submitted to the HRPO when available.

(7) The knowledge of any pending compliance inspection/visit by the FDA, DHHS Office of Human Research Protections (OHRP), or other government agency concerning this research, the issuance of Inspection Reports, FDA Form 483, warning letters or actions taken by any regulatory agencies including legal or medical actions and any instances of serious or continuing noncompliance with the regulations or requirements, must be promptly reported to the HRPO

